| 3.4. | Subject Reported Ocular Symptoms | Subjects will respond to a verbal open-ended symptoms questionnaire. | |
| 3.5. | Follow-up Questionnaire | Subjects will respond to the following questionnaires: 1. CLUE Follow-up 2. GSI Product Performance | |
| 3.6. | Entrance Visual Acuity | Record the distance Snellen visual acuity with the contact lenses (OD, OS, and OU) to the nearest letter. Subjects must read the smallest line until at least 50% of the letters are read incorrectly. | |
| 3.7. | Subjective Lens Fit Assessment | Evaluate overall lens fit acceptance (acceptable or unacceptable) based on centration, movement and other fitting characteristics. | |

| | Visit 3: Treatment 2 Follow-Up 1 | | | |
|-------|----------------------------------|---------------------------------------------------------------------------------------------------------------------------------------------------------------------------------------------------------------------------------------------------------------------------------|--|--|
| Step | Procedure | Details | | |
| | | An unacceptable fit is deemed by one of the following criteria: • limbal exposure at primary gaze or | | |
| | | with extreme eye movement edge lift excessive movement in primary and | | |
| | | up gaze insufficient movement in all three of the following conditions: primary gaze, up gaze, and Josephson push up | | |
| | | Note: if lens fit is unacceptable subject will be discontinued from the study. | | |
| 3.8. | Surface Deposits | Record any front and back surface lens deposits. | | |
| 3.9. | Lens Wettability | Record the white light lens wettability of both lenses. | | |
| 3.10. | Lens Removal & Storage | Both lenses will be removed and stored wet in a labeled container with Opti-Free® PureMoist®. The lenses can be stored refrigerated or frozen prior to shipment back to the Sponsor. Lenses will be stored at JJVC for 45 days after LSLV for laboratory testing (Section 7.4). | | |

| | Visit 3: Treatment 2 Follow-Up 1 | | |
|-------|----------------------------------|-----------------------------------------------------------------------------------------------------------------------------------------------------------------------------------------------------------------------------------------------------------------------------------------------------------------------------------------------------------------------------------------------------------------------------------------------------------------------------------------------------------------------------------------------------------------------------------------------------------------------------------------------------------------------------------------------|--|
| Step | Procedure | Details | |
| 3.11. | Slit Lamp Findings | Slit Lamp Classification Scale will be used to grade the findings. Record only whole numbers. Limbal and Bulbar Conjunctival Hyperemia findings and Corneal Staining Assessment will be emphasized using a more detailed scale. Note: Findings must be Grade 0, 1 or 2 as graded on the FDA scale (CTP-2018) to continue onto Trial Period 2. If the subject is not eligible (Grade 3 or 4), they must be followed as an adverse event. Once resolved, the subject is terminated from the study. Adverse events must be reported to the JJVC monitors immediately. If the clearance of the fluorescein needs to be expedited, preservative-free rewetting drops or saline may be instilled. | |

| | Visit 3: Treatment 3 Lens Fitting | | | |
|-------|-------------------------------------------------|-------------------------------------------------------------------------------------------------------------------------------------------------------------------------------------------------------------------------------------------------------------------------------------------------------------------------------------------------------------------------|--|--|
| Step | Step Procedure Details | | | |
| 3.12. | Lens Fitting | The Lens Randomization Table will be used to determine which study lens is worn third. The lens powers are based on the vertexed (12mm), spherical equivalent subjective refraction. The final lens power from Trial Fitting 1 or 2 can also be used. The investigator or subject will place the lenses on. Quickly check for any lens damage and replace if necessary. | | |
| 3.13. | Lens Settling | Allow the study lenses to settle for a minimum of 5 minutes. | | |
| 3.14. | Spherical Over- refraction & Optimization | Perform a spherical over-refraction OD and OS. Optimize the lens power to achieve an over-refraction of ±0.00 D OD and OS. Ensure that any new lenses are not damaged. One modification attempt will be allowed. | | |
| 3.15. | Time Interval | Please wait for at least 10 minutes from final lens insertion to continue. | | |
| 3.16. | Subject Reported Ocular Symptoms | Subjects will respond to a verbal open-ended symptoms questionnaire. | | |

| | Visit 3: Treatment 3 Lens Fitting | | | |
|-------|-----------------------------------|----------------------------------------------------------------------------------------------------------------------------------------------------------------------------------------------------------------------------------------------------------------------------------------------------------------------------------------------|--|--|
| Step | Procedure | Details | | |
| 3.17. | GSI Post-Fit Questionnaire | Subjects will respond to the GSI Post-Fit Questionnaire. | | |
| 3.18. | Visual Acuity | Record the distance Snellen visual acuity with the contact lenses (OD, OS, and OU) to the nearest letter. Smaller lines must be shown until the subject incorrectly identifies at least 50% of the letters. | | |
| 3.19. | Lens Fit Assessment | Subjective Assessment of the Lens Fit. If the fit is graded as unacceptable based on the criteria below, then the subject is discontinued from the study and will not be replaced. 1. Limbal exposure in any gaze 2. Edge lift 3. Insufficient and/or excessive movement in all three movement categories | | |
| 3.20. | Lens Wettability | Record the white light lens wettability of both lenses. | | |
| 3.21. | Continuance | For the subject to continue in the study, they must meet all three of the following criteria: 1. Visual acuity is 20/30 or better OD and OS 2. The lens fit is acceptable OD and OS 3. Investigator approval. If the Investigator does not approve the dispensing of the first study lens, then the study is terminated for that subject. | | |

| | Visit 3: Treatment 3 Lens Fitting | | |
|-------|-----------------------------------|--------------------------------------------------------------------------------------------------------------------------------------------------------------------------------------------------------------------------------------------------------------------------------------------------------------------------------------------------------------------------------------------------------------------------------------------------------------------------------------------------------------------------------------------------------------------------------------------------------------------------------------------------------------------------------------------------------------------------------------------------------------------------------|--|
| Step | Procedure | Details | |
| 3.22. | Dispense | The lenses will be dispensed for 13-15 days. The subjects should wear their lenses similar to the inclusion criteria: ≥6 hours per day, ≥5 days per week. The lenses will be worn as daily wear only. All subjects will be provided Opti-Free® PureMoist® to be used in a rub regime. Preservative-free rewetting drops are permitted if needed. The lenses must be stored in the supplied case out of direct sunlight. Note 1: In the event a lens is lost or damaged, the subject will return to the investigator site for replacement (extra lenses cannot be given at the dispensing visit). Note 2: The subject's habitual contact lenses cannot be worn at any time during the study. | |

VISIT 4

The follow-up will occur 13-15 days after the dispensing of the second study lenses. The subjects must enter the visit wearing their study contact lenses.

| | Visit 4: Treatment 3 Follow-Up 1 | | | |
|------|------------------------------------------------------------|-----------------------------------------------------------------------------------------------------------------------------------------------------------------------------------------|--|--|
| Step | Step Procedure Details | | | |
| 4.1. | Adverse Events and Concomitant Medications Review | Review the subject's concomitant medications and record any changes from the previous study visit. Record any adverse events or medical history changes from the previous study visit. | | |
| 4.2. | Wearing Time | Record the average wearing time and comfortable wearing time. | | |
| 4.3. | Compliance | Confirm compliance with the prescribed wear schedule. Outdoor and total hours will be asked. | | |
| 4.4. | Subject Reported Ocular Symptoms | Subjects will respond to a verbal open- ended symptoms questionnaire. | | |

| | Visit 4: Treatment 3 Follow-Up 1 | | |
|-------|-----------------------------------|-------------------------------------------------------------------------------------------------------------------------------------------------------------------------------------------------------------------------------------------------------------------------------------------------------------------------------------------------------------------------------------------------------------------------------------------------------------------------------------------------------------------------------|--|
| Step | Procedure | Details | |
| 4.5. | Follow-up Questionnaire | Subjects will respond to the following questionnaires: 1. CLUE Follow-up 2. GSI Product Performance | |
| 4.6. | Entrance Visual Acuity | Record the distance Snellen visual acuity with the contact lenses (OD, OS, and OU) to the nearest letter. Subjects must read the smallest line until at least 50% of the letters are read incorrectly. | |
| 4.7. | Subjective Lens Fit Assessment | Evaluate overall lens fit acceptance (acceptable or unacceptable) based on centration, movement and other fitting characteristics. An unacceptable fit is deemed by one of the following criteria: • limbal exposure at primary gaze or with extreme eye movement • edge lift • excessive movement in primary and up gaze • insufficient movement in all three of the following conditions: primary gaze, up gaze, and Josephson push up Note: if lens fit is unacceptable subject will be discontinued from the study. | |
| 4.8. | Surface Deposits | Record any front and back surface lens deposits. | |
| 4.9. | Lens Wettability | Record the white light lens wettability of both lenses. | |
| 4.10. | Lens Removal & Storage | Both lenses will be removed and stored wet in a labeled container with Opti-Free® PureMoist®. The lenses can be stored refrigerated or frozen prior to shipment back to the Sponsor. Lenses will be stored at JJVCI for 45 days after LSLV for laboratory testing (Section 7.4). | |

| Visit 4: Treatment 3 Follow-Up 1 | | | |
|----------------------------------|--------------------|------------------------------------------------------------------------------------------------------------------------------------------------------------------------------------------------------------------------------------------------------------------------------------------------------------------------------------------------------------------------------------------------------------------------------------------------------------------------------------------------------------------------------------------------------------------------------------------------------------------------------|--|
| Step | Procedure | Details | |
| 4.11. | Slit Lamp Findings | Slit Lamp Classification Scale (will be used to grade the findings. Record only whole numbers. Limbal and Bulbar Conjunctival Hyperemia findings (and Corneal Staining Assessment) will be emphasized using a more detailed scale. Note: Findings must be Grade 0, 1 or 2 as graded on the FDA scale to continue onto Trial Period 2. If the subject is not eligible (Grade 3 or 4), they must be followed as an adverse event. Adverse events must be reported to the JJVC monitors immediately. If the clearance of the fluorescein needs to be expedited, preservative-free rewetting drops or saline may be instilled. | |

FINAL EVALUATION

The final evaluation will ordinarily take place immediately following the last scheduled follow-up visit per the study protocol. It may also take place at any point the subject discontinues the study or is terminated from the study.

| Final Evaluation | | | | |
|------------------|--------------------------------------------------------------------------------------|------------------------------------------------------------------------------------------------------------------------|--|--|
| Step | Procedure | Details CTP | | |
| F.1 | Final Exam Form | Indicate if the subject completed the study successfully. If subject discontinued from the study, indicate the reason. | | |
| F.2 | Subjective Perform bare-eye subjective spherocylindrical refraction with a phoropter | | | |

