5. TEST ARTICLE ALLOCATION AND MASKING

5.1. Test Article Allocation

Use of the test articles will be randomized using a randomization scheme supplied by the study biostatistician.

This is a multi-site, double-masked, dispensing and randomized study. The study lenses will be worn in a bilateral and random fashion using a 2 treatment by 3 period (2x3) crossover design.

A block size of two (2) sequences will be utilized. A computer-generated randomization scheme will be used to randomly assign subjects, in blocks of 2, to one of the two possible lens wear sequences (TEST/CONTROL/CONTROL or CONTROL/TEST/TEST). The random scheme will be generated by site using the PROC PLAN procedure from SAS Software Version 9.4 or higher (SAS Institute, Cary, NC).

The study site must follow the randomization scheme provided and complete enrollment according to the randomization list and not pre-select or assign subjects. The randomized

assignment of subjects will be performed at the first visit prior to the first fitting. The following must have occurred prior to randomization:

- Informed consent has been obtained
- Subject meets all the inclusion / exclusion criteria
- Subject history and baseline information has been collected.

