| 1.14 | Lens Fitting | The Lens Randomization Table will be used to determine which study lens is worn second. The lens powers are based on the vertexed (12mm), spherical equivalent subjective refraction. The investigator or subject will place the lenses on. Quickly check for any lens damage and replace if necessary. | | | |
| 1.15 | Lens Settling | Allow the study lenses to settle for a minimum of 5 minutes. | | | |
| 1.16 | Spherical Over- refraction & Optimization | Perform a spherical over-refraction OD and OS. Optimize the lens power to achieve an over-refraction of ±0.00 D OD and OS. Ensure that any new lenses are not damaged. One modification attempt will be allowed. | | | |
| 1.17 | Time Interval | Please wait for at least 10 minutes from final lens insertion to continue. | | | |

| | Visit 1: Treatment 1 Lens Fitting | | | |
|------|-------------------------------------|-----------------------------------------------------------------------------------------------------------------------------------------------------------------------------------------------------------------------------------------------------------------------------------------------------------------------------------------------------------------------------------------------------------------------------------------------------------------------------------------------------------------------|--|--|
| Step | Procedure | Details | | |
| 1.18 | Subject Reported Ocular Symptoms | Subjects will respond to a verbal open-ended symptoms questionnaire. | | |
| 1.19 | GSI Post-Fit Questionnaire | Subjects will respond to the GSI Post-Fit Questionnaire. | | |
| 1.20 | Visual Acuity | Record the distance Snellen visual acuity with the contact lenses (OD, OS, and OU) to the nearest letter. Smaller lines must be shown until the subject incorrectly identifies at least 50% of the letters. | | |
| 1.21 | Lens Fit Assessment | Evaluate overall lens fit acceptance (acceptable or unacceptable) based on centration, movement and other fitting characteristics. An unacceptable fit is deemed by one of the following criteria: Iimbal exposure at primary gaze or with extreme eye movement edge lift excessive movement in primary and up gaze insufficient movement in all three of the following conditions: primary gaze, up gaze, and Josephson push up Note: if lens fit is unacceptable subject will be discontinued from the study. | | |

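### Step 1.14, the first lens fitting, tells the site to look up the lens worn second, which contradicts the sequences in Sections 4.1 and 5.1

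*Combined protocol and SAP*

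**What the plan says.** Sections 4.1 and 5.1 define a two-treatment, three-period crossover. Each subject is randomized, before the first fitting, to "one of the two possible lens wear sequences (TEST/CONTROL/CONTROL or CONTROL/TEST/TEST"). Allocation is balanced within site: "A block size of two (2) sequences will be utilized".

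Section 7.2 gives the site its step-by-step instructions. Under "Visit 1: Treatment 1 Lens Fitting", step 1.14 reads "The Lens Randomization Table will be used to determine which study lens is worn second", and the lenses are then placed on the eye. Step 2.12, at the Treatment 2 fitting, repeats that sentence word for word. Step 3.12, at the Treatment 3 fitting, reads "The Lens Randomization Table will be used to determine which study lens is worn third".

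Other steps in Section 7.2 name a period or lens that does not fit their visit:

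- Step 3.11, at the end of the second wearing period, states: "Findings must be Grade 0, 1 or 2 as graded on the FDA scale (CTP-2018) to continue onto Trial Period 2". Step 4.11, at the final visit, gates entry to the same period.
- Step 3.21, at the third fitting, states: "If the Investigator does not approve the dispensing of the first study lens, then the study is terminated for that subject". Step 2.21, at the second fitting, also speaks of the first lens.
- The introduction to Visit 4 counts its window from dispensing of the second lenses, although a third pair is dispensed at Visit 3.

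**The concern.** Step 1.14 is the instruction in the visit schedule that says which lens goes on the eye in Period 1. As written, it points to the second position of the assigned sequence. In both sequences that position holds the other lens, so a subject fitted from it gets the wrong lens in Period 1. Steps 2.12 and 3.12 agree with Section 5.1, so step 1.14 is the only faulty look-up, but it is enough to remove the within-subject switch.

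The primary analysis depends on that switch. Section 14.5 fits sequence, period, lens type and first-order carryover as fixed effects, and a subject who wears one lens throughout contributes no within-subject comparison of lenses.

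**Working it through.** The plan states no figure on this point. The check traces the instructions and then tests whether the planned model can be fitted.

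**1. Trace of the look-ups (steps 1.14, 2.12, 3.12)**

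| Assigned sequence | Visit 1: position 2 | Visit 2: position 2 | Visit 3: position 3 | Delivered |
|---|---|---|---|---|
| T/C/C | C | C | C | C/C/C |
| C/T/T | T | T | T | T/T/T |

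**2. Estimability under Section 14.5**

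The fixed-effects columns are intercept (1), sequence (1), period (2), lens (1) and carryover (1, set to zero in Period 1), six in all. Site and the baseline covariate are left out.

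- T/C/C and C/T/T: rank 6 of 6, so the lens effect is estimable.
- C/C/C and T/T/T: rank 5 of 6. The lens column duplicates the sequence column, so the lens effect is not estimable.

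**3. What could be salvaged if every subject were affected**

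Suppose sequence and carryover were dropped and the 80 completers compared as two parallel groups of 40 on the three-period mean. Inputs from Section 14.2 are variance V and covariance C of 349.3 and 110.9 (comfort) and 257.4 and 82.1 (vision). The margin is 5 points, with a two-sided 95% interval.

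Parallel groups, SE = √[2 × (V + 2C)/3 / 40]:

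- Comfort: (349.3 + 221.8)/3 = 190.4; SE = √(2 × 190.4/40) = 3.09
- Vision: (257.4 + 164.2)/3 = 140.5; SE = √(2 × 140.5/40) = 2.65

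Intended crossover, lens as the only fixed effect as in Section 14.2, SE = √{(V − C) / [40 × (1.5 − 0.5k)]} with k = C/(V + 2C):

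- Comfort: k = 110.9/571.1 = 0.194; SE = √(238.4/56.12) = 2.06
- Vision: k = 82.1/421.6 = 0.195; SE = √(175.3/56.11) = 1.77

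Power with no true difference is Φ(5/SE − 1.96). The last two columns use the noncentral t instead.

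| Domain | Crossover, normal | Parallel, normal | Crossover, t | Parallel, t |
|---|---|---|---|---|
| Comfort | 68% | 37% | 67% | 36% |
| Vision | 81% | 47% | 80% | 46% |

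**4. If only some subjects were affected**

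In the Section 14.5 fixed-effects model with compound symmetry, the lens estimate is the difference between sequences in the mean of (2p₁ − p₂ − p₃)/4, where p₁, p₂ and p₃ are a subject's scores in Periods 1, 2 and 3. A subject who wears one lens throughout contributes zero lens difference to that contrast. If a fraction f in each sequence is affected and analysed as randomized, with no true carryover, the expected estimate is (1 − f) times the true difference. The documents do not give f, so these values are assumptions: f = 0 leaves a true −5 at −5, f = 5% gives −4.75 and f = 10% gives −4.5. The shift is toward zero, which favours a non-inferiority claim when the test lens is worse.

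**The case against.** The strongest reply is that nobody is likely to be misled. The step sits under a Treatment 1 heading, and step 1.23 in the same block calls the lens the first study lens. Section 5.1 requires the site to follow the randomization scheme. Section 5.3 separately sets out dispensing: consult the scheme for the subject's assignment, record the subject on the matching line, pull the corresponding articles and log every opened lens. This stands. The sentence looks like a copy of step 2.12, and the design described in Sections 4.1, 4.2 and 5.1 is consistent.

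A reader might infer three stronger things that the documents do not support.

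- **That the crossover is in fact lost.** This would need sites generally to ignore the heading, step 1.23, Section 5.1 and Section 5.3.
- **That masking would hide a swap from the site.** Section 5.2 hides what codes P and W mean, not the codes, which are printed on the blister label. Giving one code three times against a line that lists two codes would be visible, and Section 6.7 has the monitor reconcile the articles.
- **That power would fall from Table 5's 93% and 98% to the parallel-group values.** That is not like for like. With the same matrices and 80 completers in total, the intended crossover gives about 67% and 80%. The gap between those values and Table 5 is a separate question and does not come from step 1.14.

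The other stale steps (2.21, 3.11, 3.21, 4.11 and the Visit 4 introduction) do not decide which lens is given. They belong in the same edit but add no weight to the allocation point.

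**Conclusion.** The contradiction is real and in current, operative text. Step 1.14 names the wrong position in the sequence, and no fitting step in Section 7.2 names the right one. It is an internal inconsistency, not a weakness of the design.

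The consequence is conditional. Under universal literal compliance the lens effect in Section 14.5 is not estimable. A salvage parallel-group analysis would have about 36% power for comfort and 46% for vision, against about 67% and 80% for the intended crossover on the same inputs. Those powers assume 40 completers per sequence, the compound-symmetric matrices of Section 14.2 and no true difference. The loss of estimability needs none of these assumptions. Partial error would shrink the estimate toward zero under the conditions stated in the working.

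The likelihood of any error cannot be quantified. The layout of the randomization table is not shown, and the surrounding text points sites to the correct lens. The correction is still worth making: error is unlikely, but it would be serious and the edit is trivial.

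**What to change.** Reconcile step 1.14 with Section 5.1, so that the Treatment 1 fitting uses the lens listed for Period 1 of the assigned sequence, that is, the lens worn first.

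In the same edit, reconcile the period or lens named in steps 2.21, 3.11, 3.21, 4.11 and the Visit 4 introduction with the visit at which each applies. The content of those continuation rules is for the sponsor to settle; the point here is only that their wording does not match their visit.

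The cost is one word in step 1.14 and a few matching phrases. No subjects, visits, data or analyses are added.
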